#### Specific Aims

**R21 Specific Aims:** This phase will determine the dose-response curve to OT for proposed measures of target engagement (i.e., mu suppression and pupillary dilation). The proposed study will use a single administration, within-subjects, crossover design to model the dose-response to OT across a large range of doses. Subjects with schizophrenia will be randomized to either: 8, 12, 24, 36, 48, 60, 72, or 84 IU OT (6 subjects to each dose). Each subject will receive OT and placebo in administrations separated by one week in randomized order. 30 minutes following OT administration, mu suppression and pupillary response will be assessed. We will also collect data on two measures of social salience (operationally defined here as behavioral tasks of social preference) to examine their correlations with measure of target engagement.

**Aim 1.** To determine the dose-response relationship OT versus placebo for measures of target engagement.

H1: At the optimal level of OT we will observe significant effects on □-suppression.

H2: At the optimal level of OT we will observe significant effects on pupillary dilation.

A Go/No Go decision will be based on Specific Aim 1. If either hypothesis is supported we will decide to go to the R33. Specific Aim 2 is exploratory and the results of the analysis will not be used for a Go/No Go decision.

Aim 2. To evaluate the relationship between target engagement and measures of social salience.

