**EEG mu suppression while observing biological motion** The mirror neuron system (MNS) is hypothesized to reflect the brain's ability to map visual representations of others' actions onto the motor representations in the observer of the same actions, an important mechanism underlying the capacity to understand and imitate social actions [32]. The MNS can be assessed in humans through EEG

measurements of neural oscillations in the mu range (8-13 Hz). While mu rhythms overlap in frequency with the more commonly known alpha rhythms (most apparent when the brain is “at rest”), they can be distinguished from alpha based on where on the scalp they are seen. Mu rhythms are typically seen over central scalp sites, overlaying sensorimotor cortex, whereas alpha rhythms are typically seen over occipital scalp sites. Mu rhythm amplitudes are largest when a person is at rest and *decreases* in amplitude when that person moves, observes movement, or even simply imagines moving [33]. This decrease in amplitude is called mu suppression and reflects engagement of the MNS. Mu suppression has been seen in response to a variety of stimuli, including point-light walkers depicting biological motion [32, 34]. Given that OT has been shown to increase responding to social stimuli, Perry et al. [35] examined its effects on mu suppression in healthy students when viewing stimuli depicting biological motion. The results of this study found greater mu suppression within a narrower frequency band (8-10 Hz) when subjects viewed point light biological motion than when they viewed non-biological motion (consisting of moving dots depicting a circle). Perry et al. also found that single doses of OT led to greater suppression of mu oscillations than placebo while subjects observed a point light display of a human walking.

**C.1.b Social Processing in Psychiatric Disorders** Impairments in social cognition cross diagnostic boundaries. For this research program we elected to limit the sample to diagnostic groups that had been studied using social cognition training programs that were similar to the system we plan to employ. Such studies have focused mostly on schizophrenia and schizoaffective disorders. Previous work from our group [36] found that many patients with bipolar illness had relatively preserved social cognition. As a result, we restricted the sample to include only non-affective psychotic disorders.

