**Table 2: Timeline of Oxytocin Challenge Procedures**

Time (minutes)	Procedure
0	Drug administration, setting up of EEG electrodes
30	Biological Motion Mu Suppression
45	Pupillometry Task
65	Gaze-cuing task
95	One-armed bandit task

**C.1.e. EEG Mu Suppression Task** To assess mu suppression, we will use a biological motion task in which subjects will be asked to identify either the gender, the emotion (happy or sad), or intention (moving towards or away) of a point-light walker. This paradigm has been validated in a previous study to show greater mu suppression when viewing biological versus non-biological motion, and greater mu suppression when subjects were administered OT [37]. Stimuli consist of 5 s video clips. Each video clip contains all three dimensions, e.g. a clip can show a sad woman walking toward the observer, a happy man walking away, etc. Additionally, a non-biological motion clip will be used as a control stimulus, and consists of dots moving in a circle either to the left or right of the screen. Clips will be presented on a monitor approximately 70 cm from the participant. E-Prime will be used for stimulus presentation and for syncing of triggers with the EEG equipment.

Stimuli will be presented in four separate randomized blocks, with each

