**Figure 1: Biological Motion Mu Suppression**

[figure not shown]
block consisting of a separate task, requiring the subject to identify only one dimension (e.g., identify only gender, only emotion, only intention, direction of circle). A total of 23-26 clips per block will be administered. Twenty of the clips will be of one level of the dimension (e.g., male walkers) while 3-6 clips will be of the other level (e.g., female walkers). The participants are instructed to silently count the number of occurrences of the rare event and report this at the end of the block to ensure that they are attending to the task. This task will take approximately 15 minutes to complete.

EEG data will be initially filtered with a 0.5 Hz high-pass filter and re-referenced to the mastoids. Eyeblinks will be corrected using standard algorithms [38]. Artifacts exceeding  $\pm 100 \mu\text{V}$  in amplitude at any electrode site will be rejected. As in prior studies the first 10 s of each block will not be analyzed to remove potential confounds of attentional shifts due to initiation of the stimuli [37, 39]. The first 2 s of each remaining 5 s clip will be analyzed [37]. A fast Fourier transform (FFT) using a Hanning window will be performed in 0.5 Hz intervals. Integrated power between 8-10, 10-12, and 15-25 Hz range will be assessed. Mu suppression will be calculated as the  $\log_{10}$  ratio of the power during the biological motion clips relative to the moving circle clips. This ratio is intended to account for individual differences in EEG power as well as normalize ratio data that are not typically normally distributed. A negative number indicates mu suppression. Six electrode sites will be examined: C3, Cz, C4 (where mu suppression is expected), and O1, Oz, and O2 (where typical alpha modulation is seen).

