EEG activity will be collected continuously throughout the session and amplified using a 64-channel BioSemi ActiveTwo amplifier (BioSemi, Germany). Data will be sampled at 1,024 Hz with filter settings of DC to 100 Hz. Sixty-four cap-mounted Ag-AgCl electrodes will be positioned using a modified international 10-20 system placement scheme. Additionally, four electrodes will be used to measure horizontal electrooculogram (EOG; placed on the outer canthus of the left and right eye) and vertical EOG (placed above and below the left eye). All electrodes will be referenced using common mode rejection during EEG recording and rereferenced offline to linked-mastoids. Data will be processed using Brain Vision Analyzer 2.

**Pilot Data:** We collected pilot data in 11 stable schizophrenia patients who were receiving an antipsychotic medication. After we obtained informed consent, subjects were administered 40 IU of OT or placebo in randomized order on 2 occasions separated by one week. The mu suppression paradigm was administered approximately 30 minutes following the nasal spray. As can be seen in Figure 1, mu suppression was greater than placebo in all three tasks, with an average effect size of  $d = 0.24$ .

**C.1.f Pupillometry Task** To assess pupil dilation to social stimuli, we will administer a facial affect identification task. This paradigm has been modified and adapted from previously published studies in healthy controls [40]. Stimuli will consist of male and female faces depicting happy, afraid, or neutral expressions, drawn from the Japanese and Caucasian Facial Expressions of Emotion and Neutral Faces dataset [41]. Additionally, the same stimuli have been scrambled to use as control stimuli. A dark grey background will be used throughout the experiment. Stimuli will be presented on a monitor approximately 70 cm from the participant. E-Prime will be used for stimulus presentation and for syncing with the pupillometry system.

Sixteen of each stimulus type will be shown in a randomized order. Each trial begins with a 3 s fixation cross followed by the presentation of the stimulus for 5 s. After stimulus offset, a screen will be shown with written options for type of stimulus. Participants will be instructed to not blink during the presentation of the fixation

[figure not shown]

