**C.1.h. Data Analysis:** The primary goal of the R21 phase is to determine the dose response curve to RT for mu suppression and pupillary response. Prior to modeling the form of the curves we will obtain descriptive statistics and graphical summaries for the measures of target engagement on placebo, at each of the active doses. We will also plot the within subject change scores and the overall dose-response curve. To formally determine whether there is target engagement we will fit a logistic dose response curve to the data for each of the outcome measures. We assume that the OT dose response curve can be adequately modeled using a 4-parameter model with a lower asymptote, slope, E50 (point of half of maximum response), and upper asymptote as the parameters. However, we will also fit a 5 parameter model that allows for an asymmetry in the acceleration and deceleration of the change slope to determine whether the additional parameter is necessary to represent the empirical dose response curve. Independent of which of the models for the dose

response curve we finally choose we will determine whether there is target engagement by testing whether the upper asymptote is significantly different from zero using a z-test based on the parameter estimate and its standard error. Specifically this test allows us to determine whether there is a measurable change in the outcome variable of interest at the optimum dose of OT (where the upper asymptote is reached) while borrowing strength across all the measurement points. For the secondary aim, examining the relationship between target engagement and social salience we will use multiple linear regression models with the social salience measures as the outcomes and change in pupillary response and mu suppression in response (OT vs placebo) as the predictors, adjusted for OT dose.

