**C.1.i. Go/No Go decision: After all 48 subjects have completed the OT challenge, we will evaluate** whether the dose response curves for pupillary response or EEG mu suppression show significant target engagement on OT relative to placebo. If there is a significant departure from placebo on either measure of target engagement, the R33 will be initiated.

**D. Milestones and Timeline:** As noted in the timeline, we anticipate that the start-up for the R21 will be accomplished in 3 months. We view this as feasible since all of the assessments – including the target engagement measures – have already been administered in our group. The 2 month start up of the R33 is also feasible since our group therapists are experienced in social cognition training. The rates of subject recruitment required for the R21 and the R33 are similar to recent studies completed by our group.

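### The Go rule states no direction and no alpha, so followed literally it would start the R33 on weakened mu suppression, the opposite of the mu hypothesis

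*Combined protocol and SAP*

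**What the plan says.** Two places make either measure sufficient. Specific Aims: "If either hypothesis is supported we will decide to go to the R33". C.1.i: "If there is a significant departure from placebo on either measure of target engagement, the R33 will be initiated".

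The test is in C.1.h: "we will determine whether there is target engagement by testing whether the upper asymptote is significantly different from zero using a z-test". H1 and H2 add no sign; H2, for example, reads "At the optimal level of OT we will observe significant effects on pupillary dilation". Neither these sections nor the Power section gives an alpha, a sidedness or an adjustment for having two chances.

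For mu, the rest of the protocol is directional. C.1.a reports that in healthy students "single doses of OT led to greater suppression of mu oscillations than placebo". C.1.e describes the paradigm as validated to show "greater mu suppression when subjects were administered OT", sets the scale ("A negative number indicates mu suppression") and reports that in the pilot "mu suppression was greater than placebo in all three tasks".

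For the pupil, C.1.a cites more dilation on OT during an emotion recognition task. The C.1.f pilot (d = .81, the basis of the 84% power) found less dilation on OT to fearful faces.

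**The concern.** The decision to start the R33 (N = 120 in Table 4) rests on a test that is indifferent to sign. For the pupil that can be defended. For mu it cannot easily be, because the rationale, the scale and the pilot all point to more suppression. A real or chance weakening of suppression would still satisfy the rule as written.

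The deciding outcome is also open. C.1.e lists three frequency bands, two of them (8-10 and 10-12 Hz) inside the 8-13 Hz mu range given in C.1.a, and three central electrodes. The Power section points to an average over tasks for mu, but no band or site average is named as decisive, and no stimulus contrast is named for the pupil. With alpha, sidedness and outcome all unstated, the error rate of the gate is not fixed before the data are seen.

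**Working it through.** **The plan's own figures.** The Power section gives 84% (d = .81) and 92% (d = 1.22) for the pupil, and 89% (d = 1.03) and 45% (d = .24) for mu. They cannot be reproduced exactly, because alpha, sidedness, E50, slope and lower asymptote are not given. Simulating the 8 × 6 design with a four-parameter logistic fit under several assumed curves gave about 78-90% at d = .81 (two-sided 0.05). At d = .24 it gave 20-34% two-sided and 38-39% one-sided, against the stated 45%. This does not settle which sidedness was used, and it does not show the stated powers to be wrong.

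**False-Go rate, illustration.** Assumptions: one test per measure, correct size, two-sided 0.05, jointly normal statistics.

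| Rule | Independent | r = 0.5 | r = 0.8 |
|---|---|---|---|
| As written: 1 − 0.95² | 9.75% | 9.1% | 7.8% |
| Part due only to weakened mu: 0.025 × 0.95 | 2.4 points | 2.0 | 1.4 |
| Mu directional (\|z\| > 1.96), pupil two-sided 0.05: 1 − 0.975 × 0.95 | 7.4% | 7.0% | 6.4% |
| Mu directional, pupil two-sided 0.025: 1 − 0.975² | 4.9% | 4.7% | 4.3% |

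**Why 9.75% is not a ceiling.**
- Three independent mu tests plus one pupil test would give 1 − 0.95⁴ = 18.5%.
- In null simulations of the logistic fit, the nominal 5% z-test had a size between 3.3% and 14.3%, depending on the assumed fitting bounds and variances. Two independent measures at those sizes give 1 − 0.967² = 6.5% and 1 − 0.857² = 26.6%. The fitting settings are assumptions, so this shows only that the size needs checking.

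**Power cost.** Solve for the mean of z from each stated power, then re-evaluate at the new threshold (normal approximation).

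*If the stated powers were two-sided 0.05:*
- The mean of z is 1.834 for 45% and 3.186 for 89%. The power lost by dropping the wrong tail is Φ(−1.96 − 1.834) = 0.00007, or 0.007 percentage point, at 45%, and far less at 89%.
- Pupil at |z| > 2.24: 84% (mean 2.954) becomes 76%, and 92% (mean 3.365) becomes 87%.

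*If they were one-sided 0.05 (mean = 1.645 + Φ⁻¹(power)):*
- Mu at |z| > 1.96: 45% (mean 1.519) becomes 33%, and 89% (mean 2.871) becomes 82%.
- Pupil at |z| > 1.96: 84% (mean 2.639) becomes 75%, and 92% (mean 3.050) becomes 86%. At |z| > 2.24 they become 65% and 79%.

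**Chance of a Go under the pilot effects** (stated powers at face value, independent measures). As stated it is 1 − 0.55 × 0.16 = 91%. With directional mu and pupil two-sided 0.025 it is 1 − 0.55 × 0.238 = 87% if the powers were two-sided, or 1 − 0.670 × 0.345 = 77% if they were one-sided.

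**The case against.** The strongest reply is that the opening summary describes target engagement as OT reaching the brain and influencing social processes. On that definition a reliable change in either direction could count. This makes the point arguable but does not rescue the mu rule: A.4 treats the measures as reflecting resources allocated to social information, and C.1.a ties engagement of the mirror neuron system to suppression.

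A second reply is that a one-sided test in the hypothesised direction may have been intended. The wrong-direction component would then vanish, but the text does not say so. C.1.i does ask for significant target engagement, but C.1.h defines that term without a sign.

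Third, this is an internal gate. The Duration of Research section says that the R33 would need a new IRB submission, so a Go is not the only step before it. How strict such a gate should be is partly a judgement, and that stands: halving the pupil alpha is a choice, not a requirement.

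Two stronger readings are tempting. A reader might infer that the gate's error rate is at most 9.75%; the documents do not secure the single, correctly sized test per measure that this bound needs. A reader might also infer that C.1.a and C.1.f contradict each other on the pupil. They report different conditions, so a two-sided pupil test is acceptable.

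**Conclusion.** The point holds for the text: either measure, either direction, no alpha and no sidedness. Followed literally, weakened mu suppression is a Go, contrary to the protocol's own mu hypothesis. The sizes are illustrative. The 9.75% and the 2.4 points assume independent measures with one correctly sized two-sided 0.05 test each, and both shrink with positive correlation. The actual false-Go rate of the plan is unknown, because the deciding outcomes are not named and the behaviour of the z-test on a fitted asymptote with 6 subjects per dose has not been shown. Nothing here establishes that the sponsor meant a weakening to count as success. The gap should be closed before data lock.

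**What to change.** Before data lock:

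1. **Mu.** Go only if the OT-minus-placebo upper asymptote is in the direction of greater suppression, tested once, on one named band averaged over C3, Cz and C4 and the three biological-motion tasks. Other bands, sites and tasks are supportive.
2. **Pupil.** Name one stimulus contrast and its sidedness for the Go test. Two-sided is acceptable.
3. **Error rate.** State the alpha per measure and the sidedness behind the stated powers. Report the gate's false-Go rate from a null simulation of the planned logistic fit, not from the nominal figure. For reference, the nominal rate is 7.4% with directional mu at |z| > 1.96 and pupil two-sided 0.05, or 4.9% if the team opts for pupil two-sided 0.025.

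The cost is wording, one null simulation, and a new pupil power simulation if the named contrast differs from the pilot's. A mu effect in the opposite direction would no longer trigger a Go. If the stated powers were two-sided 0.05, the mu sign is almost free, and the optional pupil 0.025 lowers 84% to 76% and 92% to 87%. If they were one-sided 0.05, the losses are the larger ones worked out above, and the powers should be restated at the chosen thresholds.

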**Table 4**

Year	1, July 2015	2, July 2016	3, July 2017	4, July 2018	5, July 2019
R21 start up, IRB, training					
R21 collection		N = 48			
R21 lock & analysis Go/No Go decision					
R33 start up					

R33 collection			N = 120	
R33 lock & analysis				

**E. Resource Sharing Plan** The proposed study has a data sharing plan consistent with NIH policy. Final data that have not yet been published will be shared after acceptance of publication of the relevant paper. Data will be de-identified before sharing on a need to know basis, and on the agreement that once the data analysis is complete, the data will be returned or destroyed.

As part of the conditions of the grant from NIMH which funds this study, we have been informed that we are required to submit de-identified subject data to the National Institute of Mental Health Data Archive (NDA). The types of data we will submit include the following: demographic data, data from diagnostic and symptom assessments, and social salience / social cognition performance data, and EEG task data
